10.1.1.1 Bleeding and Suspected Bleeding Events

All bleeding events and suspected bleeding events, regardless of the need for exogenous FVIII therapy as treatment, should be captured in subject diaries and recorded on the designated bleeding eCRF. Bleeding events and suspected bleeding events should not be reported as adverse events, with the following exception:

- All bleeding events and suspected bleeding events which meet one or more of the criteria for being serious (refer to Section 10.2) should be reported as serious adverse events (whether or not they are bleeding events that are normal sequelae of hemophilia, and whether or not they required exogenous FVIII as treatment).

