7.4.1 Optional Liver Biopsy Risks and Benefits

Liver biopsy is considered a safe procedure, with serious complications occurring less than once in every 10,000 procedures ([Grant 2004](#)). Although the theoretical risks of significant complications are extremely small, the main complications would include bleeding and bile leakage. Another theoretical complication is infection at the needle insertion site; the sterile technique used makes this risk extremely small.

The most common problems include mild pain and a minor decrease in blood pressure. More serious complications, such as bleeding, infection, and injury to nearby organs, are very rare, but the subject will be monitored appropriately to ensure correct management should any of these occur. Any complications related to the liver biopsy should be reported as adverse events, as outlined in [Section 10](#). The liver biopsy is a standard investigation, and will be explained more fully by the experienced clinician performing the biopsy.

Each subject who participates in this optional sub-study will have a comprehensive pre-/post-biopsy surveillance plan according to the standard procedures at the institution. Timing of the liver biopsies will occur at Weeks 26, 52, and/or during Years 2-5. Safety will be assessed by adverse event reporting and clinical laboratory assessments. Per the Investigator's discretion and/or according to local guidelines, the subject may be kept in overnight following the liver biopsy for additional safety monitoring; such an overnight stay would not be considered a hospitalization for serious adverse event (SAE) reporting purposes (refer to [Section 10.4.1.6](#)).

There is no direct benefit from participating in this study other than contributing to understanding the mechanism of action of BMN 270. Consenting into this specific sub-study is optional and will not have any effect on the subject's continued participation in 270-303.

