Management and monitoring of reactions to corticosteroids should be determined by the Investigator's clinical judgment in consultation with the Sponsor's Medical Monitor. This includes the contraindicated use of NSAIDs during corticosteroid treatment and specific monitoring not already covered by the SoA. The use of COX-2 inhibitors, while not contraindicated during corticosteroid treatment, should be limited, if possible. Practical management to prevent complications related to oral corticosteroid therapy may be undertaken at the discretion of the Investigator (eg, evaluation of glucose intolerance, hyperlipidemia). Alternative, non-steroidal systemic immunosuppressive agents may be used, following a discussion between the Investigator and the Medical Monitor, should corticosteroid use be deemed by an Investigator to be clinically ineffective, not tolerated, and/or contraindicated. Hepatitis B status and HCV viral load will be rechecked 6 weeks after the start of oral corticosteroid/immunosuppressive agent treatment and then 1 week and 13 weeks after the completion of oral corticosteroid/immunosuppressive agent treatment in subjects with a history of hepatitis B or hepatitis C. All adverse events (including any adverse events suspected to be caused by or related to corticosteroid/immunosuppressive agent use) should be reported as outlined in Section 10 of the protocol.

Subjects on corticosteroids should receive appropriate counseling and support regarding side effects from the Investigator or the treating institution (eg, listings of side effects and when to notify carers, wallet card for emergencies if on steroids, etc.). Additional management, including the co-prescription of additional medications to prevent complications related to corticosteroid therapy, may be undertaken at the discretion of the Investigator, including, but not limited to, prophylaxis against the occurrence of gastric ulcers, osteoporosis, and infections. The above guidance should also be followed in the event that an alternative immunosuppressive agent is used, as applicable.

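### Non-serious bleeding after the optional liver biopsy must be reported as an adverse event under Section 7.4.1 and must not be under Section 10.1.1.1

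*Protocol*

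**What the plan says.** Section 10.1.1.1 covers all bleeding and suspected bleeding, whether or not FVIII was needed. These events "should be captured in subject diaries and recorded on the designated bleeding eCRF". The section continues: "Bleeding events and suspected bleeding events should not be reported as adverse events, with the following exception". The single exception is "All bleeding events and suspected bleeding events which meet one or more of the criteria for being serious", which go in as SAEs, "whether or not they are bleeding events that are normal sequelae of hemophilia, and whether or not they required exogenous FVIII as treatment".

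Section 7.4.1, on the optional liver biopsy, says that "the main complications would include bleeding and bile leakage" and that "Any complications related to the liver biopsy should be reported as adverse events", with a pointer to Section 10. It sets no seriousness threshold. It also says that safety in the sub-study is assessed through AE reporting and laboratory tests, and that the subject gains no direct benefit from taking part. If a subject is kept overnight for monitoring, "such an overnight stay would not be considered a hospitalization for serious adverse event (SAE) reporting purposes".

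Section 14.7 builds its event summaries from AEs, by system organ class, preferred term, relationship, seriousness and severity. The list of events of special interest in Section 10.2.1 does not include bleeding.

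**The concern.** Keeping ordinary hemophilia bleeds out of the AE tables is sensible, because they are an efficacy outcome and would swamp the safety listing. Section 10.1.1.1, however, is written for all bleeding and makes no allowance for a bleed caused by a study procedure. Section 7.4.1 wants exactly that bleed reported as an AE.

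At stake is the safety record of a research biopsy in people with a bleeding disorder. AE reporting is one of the two safety measures named for the sub-study, and bleeding is one of the two main complications named. If sites resolve the conflict differently, the number of biopsy bleeds in the AE tables will partly reflect which section each site read.

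**Working it through.** No arithmetic decides this point and the plan gives no figure to reproduce. The check sets the passages side by side.

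**1. Is the bar confined to hemophilic bleeds?** No. It applies to bleeding events without qualification. The wording of the serious exception, "whether or not they are bleeding events that are normal sequelae of hemophilia, and whether or not they required exogenous FVIII as treatment", shows that the section has bleeds in view that are not normal sequelae of hemophilia. A biopsy bleed falls within it.

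**2. Does the cross-reference in 7.4.1 resolve the conflict?** No. It tells the site to report biopsy complications in the way Section 10 sets out, and 10.1.1.1, inside Section 10, says not to report a non-serious bleed.

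**3. How is each type of biopsy event routed?**

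- Serious bleed: AE under 7.4.1, SAE under 10.1.1.1. The two agree and the event is in the safety tables.
- Non-serious bleed treated with FVIII: AE under 7.4.1, bleeding eCRF only under 10.1.1.1. Conflict.
- Non-serious bleed not treated with FVIII: the same conflict. If 10.1.1.1 is followed, the event is also outside the annualized bleeding rate, which by its definition counts only bleeds requiring FVIII. It then exists only on the bleeding eCRF.
- Bile leakage, pain or a fall in blood pressure: reportable as AEs under either section. No conflict.

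**4. What is lost when a bleed is kept off the AE eCRF?** Section 10.3.3.2 asks for CTCAE grading of AEs, SAEs and events of special interest, and Section 10.3.3.3 has causality recorded on the AE eCRF. The protocol states neither for an event held only on the bleeding eCRF. The event also falls outside the AE summaries of Section 14.7.

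**5. How many procedures could be affected?** Biopsies are offered around Week 26, around Week 52 and in Years 2-5 to approximately 20 subjects. If every subject consented once in each period, that is 3 × 20 = 60 biopsies. This is a ceiling for the scheduled biopsies, not an expectation: the procedure is optional and the periods are joined by and/or. Section 7.4.1 puts serious complications at less than once in 10,000 procedures and gives no rate for non-serious bleeding, so no number of affected events follows.

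**The case against.** The strongest reply is that 7.4.1 is specific and 10.1.1.1 is general, so a careful site would follow 7.4.1 and report the bleed. This has force. A reader might infer from 10.1.1.1 that the AE tables will show none of these bleeds, and the documents do not support that: the loss occurs only where a site follows 10.1.1.1. What stands is that the protocol does not say which section governs, and the section a site consults when completing AE forms is the one that says not to report.

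A second reply is that only minor events are affected. Serious bleeds are SAEs. Section 10.2 counts important medical events as serious and treats complications during hospitalization as AEs. The overnight-stay provision is for monitoring and does not excuse a stay prolonged by a complication. This is right and limits the consequence, but 7.4.1 asks for any complication, not only serious ones.

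Two wider readings are tempting and should not be drawn.

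- **Steroid-related gastric bleeding.** A reader might infer the same contradiction with Section 9.4.8.2.2, which mentions "prophylaxis against the occurrence of gastric ulcers, osteoporosis, and infections". That section names ulcers, not bleeding, and defers to Section 10 for reporting. Section 10.4.1.1 asks for the diagnosis rather than the sign, so an ulcer can itself be the AE.
- **Bleeding-rate endpoint.** A reader might infer that each FVIII-treated biopsy bleed inflates a subject's annualized rate by a fixed amount. The current window runs from Week 5, or from Week 27 after prior emicizumab, to the last visit by data cutoff. Its length varies by subject, many biopsies in Years 2-5 may fall after the cutoff, and the handling of procedural bleeds may properly be left to the SAP.

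**Conclusion.** The contradiction is real, stands in the current text and is narrow: a non-serious bleed after the optional liver biopsy is an AE under Section 7.4.1 and not one under Section 10.1.1.1. The consequence is inconsistent capture between sites of a main harm of a procedure with no direct benefit. It is not a demonstrated loss of all such events.

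Serious bleeds are unaffected, and non-serious bleeds remain on the bleeding eCRF. The primary endpoint is untouched. The number of events cannot be estimated from the protocol, and with an optional procedure in about 20 subjects it may be small. The conclusion rests on reading 10.1.1.1 as covering all bleeding, which its own wording supports. An SAP could tabulate the bleeding eCRF, but it could not tell sites what to enter on the AE eCRF, so the correction belongs in the protocol.

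**What to change.** Reconcile the two sections with one sentence in 10.1.1.1, added as a second exception: bleeding related to a study procedure, such as the liver biopsy, is reported as an AE regardless of seriousness, consistent with 7.4.1. Keep the event on the bleeding eCRF as well, with a flag marking it as procedure-related. The flag is useful because the causality guidance in Section 10.3.3.3 covers the study drug, corticosteroids and other immunosuppressive agents, but not procedures.

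The cost is one sentence in the protocol, one field on an existing form and possibly a few extra AE entries. The events are already collected. This is a reporting rule and changes nothing in how subjects are treated.

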10.2 Serious Adverse Events

A serious adverse event (SAE) is any untoward medical occurrence that, at any dose:

- Results in death
- Is life-threatening

Note: Life-threatening refers to an event in which the subject was at risk of death at the time of the event. It does not refer to an event, which hypothetically might have caused death, if it were more severe.

- Requires inpatient hospitalization or prolongation of existing hospitalization

Note: In general, hospitalization signifies that the subject has been detained (usually involving at least an overnight stay) at the hospital or emergency ward for observation and/or treatment that would not have been appropriate in the physician's office or outpatient setting. If the investigational product preparation, infusion, and post-infusion observation period require transfer to an inpatient setting for completion, in the absence of an AE, this will not be considered an SAE.

Complications that occur during hospitalization are AEs. If a complication prolongs hospitalization, the event is serious.

Hospitalization for elective treatment of a pre-existing condition that did not worsen from baseline is not considered an AE.

- Results in persistent or significant disability or incapacity
- Is a congenital anomaly or birth defect in the child or fetus of a subject exposed to IP prior to conception or during pregnancy
- Is an important medical event or reaction – that, based on medical judgment, may jeopardize the subject or require medical/surgical intervention to prevent one of the other outcomes listed above (eg, anaphylaxis)

10.2.1 Events of Special Interest (EOSI)

The following EOSI need to be reported to the Sponsor within 24 hours of site awareness, irrespective of seriousness, severity or causality:

- Elevation of ALT > ULN or ≥ 1.5 x baseline value, regardless of whether that elevation triggers an initiation or modification of oral corticosteroid treatment
- Events potentially meeting the criteria for Hy's law (ALT or AST elevation ≥ 3 x ULN plus total bilirubin ≥ 2 x ULN)
- Thromboembolic event
- Immediate reactions: infusion-related reactions, hypersensitivity adverse events, or anaphylaxis
- Development of anti-FVIII inhibitory antibodies (inhibitors)
- Any new diagnosis of malignancy (except non-melanoma skin cancer)

10.3 Methods and Timing for Capturing and Assessing Safety Parameters

10.3.1 Adverse Event Reporting Period

The study AE reporting period is as follows:

- After informed consent but prior to initiation of study drug, only SAEs associated with any protocol-imposed interventions will be collected. AEs occurring during this time period should be recorded on the Medical History eCRF.
- After informed consent is obtained and following infusion of study drug, the reporting period for all non-serious AEs and SAEs begins and continues for approximately 5 years or until study discontinuation/termination, whichever is longer.

The criteria for determining, and the reporting of SAEs is provided in Section 10.2.

10.3.2 Eliciting Adverse Events

Care will be taken not to introduce bias when detecting AEs and/or SAEs. Open-ended and non-leading verbal questioning of the subject is the preferred method to inquire about AE occurrences. The Investigator will record all relevant AE/SAE/EOSI information in the subject's medical record and AE Case Report Form (eCRF).

10.3.3 Assessment of Seriousness, Severity, and Causality

The Investigator responsible for the care of the subject or medically qualified designee will assess AEs for severity, relationship to study drug and/or concomitantly administered corticosteroids and/or other immunosuppressive agents, and seriousness (refer to Section 10.2 for SAE definitions). These assessments must be made by a study clinician with

the training and authority to make a diagnosis (eg, MD/DO, physician's assistant, nurse practitioner, or DDS).

10.3.3.1 Seriousness

The Investigator will assess if an AE should be classified as “serious” based on the seriousness criteria enumerated in Section 10.2. Seriousness serves as a guide for defining regulatory reporting obligations.

10.3.3.2 Severity

Severity (as in mild, moderate, or severe headache) is not equivalent to seriousness, which is based on subject/event outcome or action criteria usually associated with events that pose a threat to a subject's life or functioning. The Investigator will determine the severity of each AE, SAE and EOSI using the Common Terminology Criteria for Adverse Events (NCI CTCAE) v4.03. Adverse events that do not have a corresponding CTCAE term will be assessed according to the general guidelines for grading used in the CTCAE v4.03 as stated in Table 10.3.3.2.1.

Table 10.3.3.2.1: Adverse Event Grading (Severity) Scale

Grade	Description	
1	Mild: asymptomatic or mild symptoms; clinical or diagnostic observations only; intervention not indicated	
2	Moderate: minimal, local or noninvasive intervention indicated; limiting age-appropriate instrumental activities of daily living (ADL) ^a	
3	Severe or medically significant but not immediately life-threatening: hospitalization or prolongation of hospitalization indicated; disabling; limiting self-care ADL ^b	
4	Life threatening consequences; urgent intervention indicated	Grade 4 and 5 AEs should always be reported as SAEs
5	Death related to AE	

^a Instrumental ADL refer to the following examples: preparing meals, shopping for groceries or clothes, using the telephone, managing money.

^b Self-care ADL refer to the following examples: bathing, dressing and undressing, feeding oneself, using the toilet, taking medications, not bedridden.

10.3.3.3 Causality

The Investigator will determine the relationship of an AE to the study drug and/or corticosteroids and/or other immunosuppressant agents and will record it on the source documents and AE eCRF. To ensure consistency of causality assessments, Investigators should apply the guidance in Table 10.3.3.3.1.

Table 10.3.3.3.1: Causality Attribution Guidance

Relationship	Description
Not Related	
 Exposure to the IP and/or corticosteroids and/or other immunosuppressive agents has not occurred 
OR
 
 The administration of the IP and/or corticosteroids and/or other immunosuppressive agents and the occurrence of the AE are not reasonably related in time 
OR
 
 The AE is considered likely to be related to an etiology other than the use of the IP and/or corticosteroids and/or other immunosuppressive agents; that is, there are no facts, evidence, or arguments to suggest a causal relationship to the IP and/or corticosteroids and/or other immunosuppressive agents.
Related	
 The administration of the IP and/or corticosteroids and/or other immunosuppressive agents and the occurrence of the AE are reasonably related in time 
AND
 
 The AE could not possibly be explained by factors or causes other than exposure to the IP and/or corticosteroids and/or other immunosuppressive agents 
OR

	
 The administration of IP and/or corticosteroids and/or other immunosuppressive agents and the occurrence of the AE are reasonably related in time 
AND
 
 The AE is more likely explained by exposure to the IP and/or corticosteroids and/or other immunosuppressive agents than by other factors or causes.

Factors suggestive of a causal relationship could include (but are not limited to):

- Plausible temporal relationship
- Absence of alternative explanations
- Rarity of event in a given patient or disease state
- Absence of event prior to study drug and/or corticosteroid and/or other immunosuppressive agent exposure
- Consistency with study product pharmacology
- Known relationship to underlying mechanism of study drug and/or corticosteroid and/or other immunosuppressive agent action
- Similarity to adverse reactions seen with related drug products

- Abatement of AE with discontinuation of study drug and/or corticosteroids and/or other immunosuppressive agents, and/or recurrence of AE with reintroduction of study drug and/or corticosteroids and/or other immunosuppressive agents

The Investigator's assessment of causality for individual AE reports is part of the study documentation process. Regardless of the Investigator's assessment of causality for individual AE reports, the Sponsor will promptly evaluate all reported SAEs against cumulative product experience to identify and expeditiously communicate possible new safety findings to Investigators and applicable regulatory authorities.

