WPAI+CIQ:HS	Work Productivity and Activity Impairment plus Classroom Impairment Questions: Hemophilia Specific

Definition of Terms:**Investigational Product (IP):**

“A pharmaceutical form of an active ingredient or placebo being tested or used as a reference in a clinical trial, including a product with a marketing authorization when used or assembled (formulated or packaged) in a way different from the approved form, or when used for an unapproved indication, or when used to gain further information about an approved use” (from International Conference on Harmonisation of Technical Requirements for Registration of Pharmaceuticals for Human Use ICH Harmonised Tripartite Guideline: Guideline for Good Clinical Practice E6 [ICH E6 (R2)]).

The terms “IP” and “study drug” may be used interchangeably in the protocol.

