9.3.3.1 Study Safety Evaluation Criteria

If any of the following events occur in a subject in the study who has received BMN 270 infusion, an urgent evaluation by the DMC will be required and further enrollment into the trial will be temporarily put on hold if recommended by the DMC per Section 9.1.

1. Liver dysfunction (criteria do not apply to ALT elevations with an extra-hepatic etiology):
 - ALT > 5x ULN, for more than 2 weeks
 - ALT > 3x ULN **and** (total bilirubin > 2x ULN **or** INR >1.5)
 - ALT > 3x ULN with signs and symptoms of liver dysfunction
2. The occurrence of Grade 4 or Grade 5 adverse events assessed as related to study drug (events of liver dysfunction are defined above).
3. The occurrence of an AE of hepatic failure.
4. The detection of high-titer neutralizing antibodies (>5 BU) to hFVIII following BMN 270 infusion in two subjects.
5. The occurrence of any cancer (except non-melanoma skin cancer) at any point after BMN 270 infusion.
6. The occurrence of a thromboembolic event with FVIII activity > 150 IU/dL in one subject.

If any of the following events occurs in a subject in the study who has received BMN 270 infusion, an urgent evaluation by the DMC will be required. Further enrollment into the trial will continue while DMC evaluation is ongoing, unless deemed otherwise by the DMC:

1. The detection of high-titer neutralizing antibodies (>5 BU) to hFVIII following BMN 270 infusion in one subject.

2. Occurrence of a thromboembolic event in one subject.

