14.7 Safety Analysis

All AEs will be coded to system organ class and preferred term using the current version of MedDRA. The incidence of AEs will be summarized by system organ class, preferred term, relationship to study drug, seriousness, and severity. A by-subject listing will be provided for those subjects who experience an SAE, including death, EOSI, or an AE resulting in early withdrawal from the study.

Clinical laboratory data will be summarized by the type of laboratory test. For each clinical laboratory test, descriptive statistics will be provided on Baseline as well as all subsequent visits. Descriptive statistics for physical examination results and vital signs will also be provided.

Detailed statistical methods will be provided in the SAP.

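### The causality table pools BMN 270, corticosteroids and other immunosuppressants and requires no verdict per agent, although one DMC trigger and the AE summary rest on a study-drug verdict

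*Protocol*

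**What the plan says.** Section 10.3.3 asks the investigator to assess "relationship to study drug and/or concomitantly administered corticosteroids and/or other immunosuppressive agents, and seriousness". Section 10.3.3.3 repeats the instruction: "The Investigator will determine the relationship of an AE to the study drug and/or corticosteroids and/or other immunosuppressant agents". For consistency, it directs investigators to Table 10.3.3.3.1.

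That table has two categories, and every criterion in both names the same combined exposure:

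- Not Related is met by any one of three alternatives. The first is "Exposure to the IP and/or corticosteroids and/or other immunosuppressive agents has not occurred".
- Related requires a reasonable link in time plus one of two further conditions. The weaker of these is "The AE is more likely explained by exposure to the IP and/or corticosteroids and/or other immunosuppressive agents than by other factors or causes".

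Two later uses refer to the study drug alone:

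- Section 9.3.3.1, first list, item 2, calls for urgent DMC evaluation on "The occurrence of Grade 4 or Grade 5 adverse events assessed as related to study drug".
- Section 14.7 states: "The incidence of AEs will be summarized by system organ class, preferred term, relationship to study drug, seriousness, and severity".

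Section 4 fixes the meaning of the term: "The terms “IP” and “study drug” may be used interchangeably in the protocol". Corticosteroids are not part of it.

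**The concern.** The rule that investigators are told to apply and the variable used later are not the same thing. The rule contrasts the three kinds of agent, taken together, with everything else. The DMC criterion and the AE summary need BMN 270 contrasted with everything else, including the steroid.

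The difference matters in this design. Section 9.4.8.2.1 starts every subject on prophylactic corticosteroids on the day of infusion, and Section 9.1 describes a 19-week regimen. Section 9.2 explains that there is no control group. With both exposures beginning on Day 1 and no comparison arm, the investigator's judgement is a main way to tell the two apart for an individual event. If that judgement is not recorded by agent when the event occurs, the SAP cannot restore it.

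**Working it through.** No arithmetic applies, because the point turns on wording. The check applies the table's criteria to three kinds of event and compares the result with the verdict that Sections 9.3.3.1 and 14.7 need.

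**Event A: explained by the corticosteroid and not by BMN 270.**
- Table as worded: the steroid lies inside the combined exposure, so it is not one of the other factors or causes. The weaker Related condition is met. The Not Related alternative of a different etiology is not met, because that etiology must lie outside all the named agents.
- Verdict as worded: Related.
- Verdict needed for study drug: not related to BMN 270.

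**Event B: explained by BMN 270, in a subject never given another immunosuppressant.**
- Table as worded: Related is met. If the and/or in the first Not Related alternative is read as *or*, non-exposure to the other immunosuppressant satisfies it, and one alternative is enough. Not Related is then met too.
- If it is read as *and*, that alternative fails, because the subject received both BMN 270 and a corticosteroid.
- Verdict as worded: Related, or both categories at once, depending on how the connective is read.
- Verdict needed for study drug: related to BMN 270.

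**Event C: explained by something outside all three kinds of agent.**
- Not Related under every reading, which agrees with the verdict needed.

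The table is therefore safe only for events of type C and, under one reading, type B. The possible errors run in both directions: A could raise criterion 2 wrongly, and B could let it be missed.

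**How much depends on it.**
- First DMC list in Section 9.3.3.1: six criteria. Only item 2 uses attribution. The liver, hepatic failure, inhibitor, cancer and thromboembolic criteria do not.
- Second DMC list: two criteria (inhibitor, thromboembolic event). Neither uses attribution.
- Section 14.7: relationship is one of five summary dimensions. System organ class, preferred term, seriousness and severity are unaffected.
- Sections 10.5.1 and 10.3.3.3: site reporting of SAEs and EOSI, and sponsor evaluation of SAEs, do not depend on the investigator's causality verdict.

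**The case against.** The strongest reply is that no passage says only one verdict is recorded. The and/or phrasing can be a template applied to each agent in turn, and other passages suggest that this was intended. Section 9.4.8.2.2 speaks of events suspected to be related to corticosteroid or immunosuppressant use, a footnote to Table 9.1.6 speaks of adverse events related to corticosteroid dosing, and Sections 9.3.3.1 and 14.7 themselves presuppose a study-drug verdict. On a pooled *and* reading, the non-exposure alternative would have almost no use, because AE reporting starts after infusion apart from certain pre-infusion SAEs. The AE eCRF is not shown and may already hold separate fields.

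This stands in part. A reader might infer that steroid and BMN 270 effects cannot be separated in this trial. The documents do not support that, because a per-agent reading is open and the eCRF is unknown. What the reply does not cure is the wording. The two readings give different verdicts for event A, about 15 sites must choose between them unaided, and even with separate fields the table never says that the other agents count as alternative causes.

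A second reply is that the DMC consequence is mild. A false trigger leads to an evaluation, and an enrollment hold follows only on the DMC's recommendation. Grade 4 and 5 events are always SAEs and are reported whatever their attribution, and under Section 15 the DMC reviews individual subject data in any case. This stands and limits the stakes.

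Two further inferences should be resisted:

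- The planned course covers 19/52 = 37% of the time to the Week 52 analysis. That is exposure time, not a share of misassigned events. A true BMN 270 reaction in that period would still be Related, and timing alone never suffices for Related. Table 9.1.6 is also a suggested schedule that may be adjusted.
- The lack of a summary by relationship to corticosteroids in Section 14.7 is not an error. The section defers detail to the SAP, and the safety objectives concern BMN 270 given with corticosteroids as a regimen.

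**Conclusion.** The point holds as a defect of wording with a limited consequence. Table 10.3.3.3.1 defines causality for a combined exposure, nothing requires a verdict per agent, and the criteria applied literally can misclassify in either direction the study-drug relationship on which DMC criterion 2 and the Section 14.7 summary depend. This is more than detail left to the SAP, because attribution is made by investigators under the protocol text.

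Its size cannot be put as a rate. The number affected depends on how many events have the steroid as a plausible cause and on how the eCRF records causality, and the documents give neither. What can be stated is the reach: one of the six criteria in the first DMC list, and one of the five dimensions of the AE summary, in a study where all of about 20 subjects receive both agents from Day 1. The conclusion assumes that investigators follow the table as written. If the eCRF already asks for each agent separately, the remaining fault is the missing rule for choosing between agents.

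**What to change.** 1. In Sections 10.3.3 and 10.3.3.3, require a separate Related/Not Related verdict for BMN 270, for corticosteroids and for other immunosuppressants, each recorded on the AE eCRF.
2. Reword Table 10.3.3.3.1 so that it is applied to one agent at a time, with the other agents counting among the alternative causes. Non-exposure then makes an event Not Related only to the agent not received.
3. State that item 2 of the first list in Section 9.3.3.1 and the relationship summary in Section 14.7 use the BMN 270 verdict.

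The cost is a few lines of protocol text, plus eCRF fields if they are not already separate. No endpoint, sample size or visit changes. Whether to add a table by relationship to corticosteroids can be left to the SAP; with separate verdicts recorded, it becomes possible.
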